4.3 Medical history

Relevant medical history (ocular and non-ocular) and current medical conditions will be tabulated by system organ class (SOC) and preferred term (PT) of the Medical Dictionary for Regulatory Activities (MedDRA) dictionary (Version 19.0 or a more recent version) for the

RS. The SOCs will be presented in alphabetical order. PTs will be ordered for each study treatment in decreasing proportion in the SYSTANE BALANCE study treatment group of interest (study treatment group 1).

Separate tables will be provided by study treatment for subjects with ocular and non-ocular histories and conditions. Presentation of subjects with ocular histories will be overall, i.e. event occurring in one eye or both eyes will be counted once. The presentation of the data in the tables will be based on subject rather than event counts.

Furthermore, medical history data will be listed by treatment, center, subject and eye (where applicable) for the RS.

4.4 Prior and concomitant medications

The number and percentage of subjects taking concomitant medications will be summarized for subjects in the Safety Analysis Set.

Summaries will be presented separately for prior and/ or concomitant medications.

- Prior medications will be defined as drugs taken and stopped prior to baseline.
- Any medication given at least once between baseline and the last day of study visit will be a concomitant medication, including those which were started pre-baseline and continued into the study treatment period.

Prior or concomitant medication will be identified based on recorded or imputed start dates of medication taking. The rules for imputing incomplete start dates are described in Section 12.2.2.

Medications will be identified by PT according to the World Health Organization (WHO) Drug Reference List dictionary (201603 or a more recent version).

Separate tables will be provided by study treatment for subjects with ocular and non-ocular prior and concomitant medications. Presentation of subjects with ocular prior and concomitant medications will be overall, i.e. medication administered in one eye or both eyes will be counted once. The presentation of the data in the tables will be based on subject rather than event counts. Tables will show the overall number and percentage of subjects within each study treatment group receiving at least one dose of the therapy.

Furthermore, prior and concomitant data will be listed by treatment, center, subject and eye (where applicable) for the RS.

5 Efficacy Analysis Strategy

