12.2.2.2 Concomitant medication start date

Concomitant treatments with partial start dates will have the date or dates imputed. Partial concomitant treatment start dates are imputed with reference to the first administration of study treatment (TRTSTD) in accordance with the rules outlined below.

	Day	Month	Year
Partial AE Start Date	Not used	MON	YYYY
Study Treatment Start Date (TRTSTD)	Not used	TRTM	TRTY

The following matrix explains the logic behind the imputation.

Comparison of month section	MON missing	MON<TRTM	MON=TRTM	MON>TRTM
YYYY missing	(C) Uncertain	(C) Uncertain	(C) Uncertain	(C) Uncertain
YYYY<TRTM	(D) = 01JULYYYY Before Study Treatment Start	(A) = 15MONYYYY Before Study Treatment Start	(A) = 15MONYYYY Before Study Treatment Start	(A) = 15MONYYYY Before Study Treatment Start
YYYY=TRTY	(C) Uncertain	(A) = 15MONYYYY Before Study Treatment Start	(C) Uncertain	(B) = 01MONYYYY After Study Treatment Start
YYYY>TRTY	(E) = 01JANYYYY After Study Treatment Start	(B) = 01MONYYYY After Study Treatment Start	(B) = 01MONYYYY After Study Treatment Start	(B) = 01MONYYYY After Study Treatment Start

The following table is the legend to the logic matrix.

Relationship	
Before Study Treatment start	Partial date indicates CMD start date prior to Study Treatment Start Date
After Study Treatment start	Partial date indicates CMD start date after Study Treatment Start Date
Uncertain	Partial date insufficient to determine relationship of CMD start date to Study Treatment Start Date
Imputation calculation	
NC / Blank Uncertain	No convention
(A) Before Study Treatment Start	15MONYYYY
(B) After Study Treatment Start	MAX(01MONYYYY, TRTSTD+1)
(C) Uncertain	IF CMDTYP1C IN (1, 3) THEN TRTSTD-1 ELSE IF CMDTYP1C IN (. 2) THEN TRTSTD+1
(D) Before Study Treatment Start	01JULYYYY
(E) After Study Treatment Start	01JANYYYY

To compute concomitant start date:

1. If the concomitant start date year value is missing, the imputed concomitant start date is set to one day prior to study treatment start date.
2. If the concomitant start date year value is less than the study treatment start date year value, the concomitant started before study treatment. Therefore:
 - a. If the concomitant month is missing, the imputed concomitant start date is set to the mid-year point (01JULYYYY).
 - b. Else if the concomitant month is not missing, the imputed concomitant start date is set to the mid-month point (15MONYYYY).

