3. If the concomitant start date year value is greater than the study treatment start date year value, the concomitant started after study treatment. Therefore:
 - a. If the concomitant month is missing, the imputed concomitant start date is set to the year start point (01JANYYYY).
 - b. Else if the concomitant month is not missing, the imputed concomitant start date is set to the month start point (01MONYYYY).
4. If the concomitant start date year value is equal to the study treatment start date year value:
 - a. And the concomitant month is missing or the concomitant month is equal to the treatment start date month, then the imputed concomitant start date is set to one day prior to study treatment start date.
 - b. Else if the concomitant month is less than the treatment start date month, the imputed concomitant start date is set to the mid-month point (15MONYYYY).

- c. Else if the concomitant month is greater than the treatment start date month, the imputed concomitant start date is set to the month start point (01MONYYYY).

If complete (imputed) concomitant end date is available and the imputed concomitant start date is greater than the (imputed) concomitant end date, then imputed concomitant start date should be set to the (imputed) concomitant end date.

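### SAP 4.4 identifies prior and concomitant medication by start date although its definitions turn on when use stopped, and SAP 12.2.2.2 gives two conflicting rules for some missing start dates

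*SAP*

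**What the plan says.** SAP 4.4 gives two definitions. For prior use: "Prior medications will be defined as drugs taken and stopped prior to baseline". Concomitant use is any medication given at least once between baseline and the last study visit, "including those which were started pre-baseline and continued into the study treatment period". The sentence that follows states how records are to be sorted: "Prior or concomitant medication will be identified based on recorded or imputed start dates of medication taking". The only imputation it points to is for start dates: "The rules for imputing incomplete start dates are described in Section 12.2.2". Section 12.2.2 also contains end-date rules (12.2.2.1), but 4.4 does not mention them.

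SAP 12.2.2.2 handles partial start dates twice. In the matrix, the uncertain cells are marked (C), and the legend reads "IF CMDTYP1C IN (1, 3) THEN TRTSTD-1 ELSE IF CMDTYP1C IN (. 2) THEN TRTSTD+1". The numbered rules below it make no use of the code. Rule 1 reads: "If the concomitant start date year value is missing, the imputed concomitant start date is set to one day prior to study treatment start date". Rule 4a covers a start in the treatment year whose month is missing or is the month of first treatment, and ends "then the imputed concomitant start date is set to one day prior to study treatment start date". The SAP does not define CMDTYP1C.

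**The concern.** The definitions in 4.4 need to know whether use had ended before baseline. The sorting sentence uses a date that does not carry that information. Taken literally, it moves every drug begun before baseline into the prior table, including drugs still in use throughout treatment.

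The protocol lets such drugs continue. Exclusion 12 bars systemic drugs known to cause dry eye only when used for less than 1 month. Exclusion 16 bars topical ocular drugs begun within 2 weeks before Screening, so longer-standing ones may continue unless another criterion, such as exclusion 1, bars them. The concomitant table is the planned by-arm summary of other treatment over the 35 days, and these are drugs a reader would look for there.

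The second problem concerns reproducibility. Two programmers, one working from the matrix and one from the numbered rules, would assign different start dates to some records. If class follows start date, they would produce different tables.

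**Working it through.** The plan gives no figure on this point to reproduce. The check compares its rules.

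**Step 1: the sorting sentence against the definitions.** For treated subjects, SAP 2.2 sets baseline at the date of first study treatment, which is TRTSTD. Take TRTSTD = 15 June 2017 and a drug with a complete start date of 1 March 2017, so that no imputation is involved.

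| End of use | By start date only | By the 4.4 definitions |
|---|---|---|
| Stopped 10 May 2017 | prior | prior |
| Stopped 1 July 2017 | prior | concomitant |
| Ongoing | prior | concomitant |
| Unknown, not recorded as ongoing | prior | cannot be decided |

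The two approaches contradict each other in rows 2 and 3, even with complete dates.

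**Step 2: the matrix against the numbered rules.** There are 4 year states (missing, earlier, equal, later) and 4 month states (missing, earlier, equal, later), giving 16 cells.

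| Cells | Matrix, code 1 or 3 | Matrix, code 2 or missing | Numbered rules |
|---|---|---|---|
| Year missing (4 cells) | TRTSTD-1 | TRTSTD+1 | TRTSTD-1 |
| Same year, month missing (1 cell) | TRTSTD-1 | TRTSTD+1 | TRTSTD-1 |
| Same year, same month (1 cell) | TRTSTD-1 | TRTSTD+1 | TRTSTD-1 |
| Remaining 10 cells | as numbered rules | as numbered rules | mid-year, mid-month, or first of year or month |

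For code 2 or missing, 4 + 1 + 1 = 6 of 16 cells disagree. For codes 1 and 3, none do. In the example the six cells give 16 June under the matrix and 14 June under the rules, on opposite sides of first treatment. In the later-month cells the matrix takes the later of the first of the month and TRTSTD+1. Because the month is later than that of first treatment, this is the first of the month, as in the rules.

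**Step 3: does the imputation conflict change the class?** Take a start in 2017 with month missing and code 2 or missing.

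| End of use | Start-date sorting: rules / matrix | 4.4 definitions: rules / matrix |
|---|---|---|
| Stopped 10 May 2017 | prior / prior | prior / prior |
| Stopped 1 July 2017 | prior / concomitant | concomitant / concomitant |
| Ongoing | prior / concomitant | concomitant / concomitant |
| Unknown, not ongoing | prior / concomitant | cannot be decided / concomitant |

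In the first row the last paragraph of 12.2.2.2 resets the imputed start to the end date, so both versions agree. Under the definitions, the choice of version matters only in the last row.

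**The case against.** The strongest reply is that the explicit definitions govern. The second one names drugs begun before baseline and continued, so a programmer who filed them as prior would break the written definition. Section 12.2.2, which 4.4 cites, also supplies end-date imputation in 12.2.2.1. On this view the start-date sentence is incomplete drafting about partial dates. Most of this stands: a programmer who follows the definitions and uses the end dates avoids most of the problem. What remains is that the sentence is the only stated sorting method and conflicts with the definitions beside it.

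A reader might infer four stronger things that the documents do not support.

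- *That concomitant use is misreported, or that all continuing drugs are misfiled.* This follows only if the start-date sentence is allowed to override the definitions.
- *That the imputation conflict generally changes class.* Step 3 shows that it does so only under start-date sorting, or when start and end are both unknown.
- *That any drug begun during treatment with its day missing is filed as prior by the numbered rules.* Rule 4a catches only starts in the calendar month of first treatment. Rule 4c dates later-month starts after it.
- *That the share of treatment days in the first-treatment month is an error rate.* Assume first-treatment dates spread evenly over 2016-2017. A month of L days leaves on average (L-1)/2 days, so the two years give (5,401 + 5,373)/731 = 14.74 days, and 14.74/35 = 42%. That is only the chance that a drug begun at a uniformly random time in the 35 days starts in that month. A conflict also needs a missing day and a code of 2 or missing, and the documents give neither frequency.

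It is also fair to say that SAP 4.4 lists all prior and concomitant data by treatment, center and subject for the Randomized Set, so the individual records remain visible.

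**Conclusion.** Both inconsistencies are in the text. The sorting sentence in SAP 4.4 conflicts with the definitions it is meant to apply, and if programmed as written it files continuing pre-baseline drugs as prior. In SAP 12.2.2.2 the matrix and the numbered rules disagree in 6 of 16 cells when CMDTYP1C is 2 or missing, and in none when it is 1 or 3.

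The point is minor. It touches the descriptive prior and concomitant medication tables only, not the noninferiority analysis, the superiority tests, the type I error rate or the sample size. How many records are affected depends on how often dates are partial, how the codes are distributed and how the programmer reads 4.4, and none of these is in the documents.

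**What to change.** In SAP 4.4, replace the start-date sentence. Class should follow the recorded or imputed end date (12.2.2.1) or ongoing status, together with the start date: prior if use stopped before baseline, concomitant if the drug was used at least once between baseline and the last study visit. Cite 12.2.2.1 as well as 12.2.2.2.

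State how a record is classed when its end date is set to NULL under 12.2.2.1 and it is not ongoing. A default of concomitant for anything not known to have stopped would settle these records silently and would lose the last-visit limit, so the choice should be written down.

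In 12.2.2.2, keep one rule for the uncertain cells, either the matrix or numbered rules 1 and 4a, and delete the other. If the matrix is kept, define the CMDTYP1C codes.

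The cost is a few lines of SAP wording and no new data. SAP 11.1 states that the database is not yet locked and the treatment code is unbroken, so the change can be made while the study is still masked.

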5.1 Efficacy Endpoints

[figure not shown]
Primary Endpoint

[figure not shown]
- Change from baseline in TFBUT (seconds) at Day 35 (Visit 3) (non-inferiority)
 - TFBUT is the mean of the available measurements (maximum of 3 readings, minimum of 1 reading) for the analysis eye

Secondary Endpoints

- Change from baseline in TFBUT (seconds) at Day 35 (Visit 3) (superiority)
- Change from baseline in Global Ocular Discomfort VAS score at Day 35 (Visit 3) (superiority)
 - The overall score is a composite of the 2 scores (frequency and severity of ocular discomfort) using the following equation:

$$VAS\ Global\ Discomfort\ Scale = \sqrt{VAS\ Frequency\ Score \times VAS\ Severity\ Score}$$

5.2 Efficacy Hypotheses

The primary efficacy hypothesis to be tested is that SYSTANE BALANCE is non-inferior to REFRESH OPTIVE Advanced/ OPTIVE PLUS (UK) with respect to the change from baseline in TFBUT at Day 35 (Visit 3). The null and alternative hypotheses are:

$$H_0: \mu_{SB} - \mu_{OA} \leq -1$$

$$H_1: \mu_{SB} - \mu_{OA} > -1$$

where μ_{SB} and μ_{OA} denote the mean change from baseline in TFBUT at Day 35 (Visit 3) in the analysis eye for SYSTANE BALANCE and REFRESH OPTIVE Advanced/ OPTIVE PLUS (UK), respectively.

The secondary efficacy hypotheses to be tested are that:

- SYSTANE BALANCE is superior to REFRESH OPTIVE Advanced/ OPTIVE PLUS (UK) with respect to the change from baseline in TFBUT at Day 35 (Visit 3)
 - The null and alternative hypotheses are:

$$H_0: \mu_{SB} - \mu_{OA} \leq 0$$

$$H_1: \mu_{SB} - \mu_{OA} > 0$$

where μ_{SB} and μ_{OA} denote the mean change from baseline in TFBUT at Day 35 (Visit 3) in the analysis eye for SYSTANE BALANCE and REFRESH OPTIVE Advanced/ OPTIVE PLUS (UK), respectively.

- SYSTANE BALANCE is superior to REFRESH OPTIVE Advanced/ OPTIVE PLUS (UK) with respect to the change from baseline in Global Ocular Discomfort VAS score at Day 35 (Visit 3)

- The null and alternative hypotheses are:

$$H_0: \mu_{SB} - \mu_{OA} \leq 0$$

$$H_1: \mu_{SB} - \mu_{OA} > 0$$

where μ_{SB} and μ_{OA} denote the mean change from baseline in Global Ocular Discomfort VAS score at Day 35 (Visit 3) in the analysis eye for SYSTANE BALANCE and REFRESH OPTIVE Advanced/ OPTIVE PLUS (UK), respectively.

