11.4.2.1 Statistical Hypotheses

The hypotheses for the secondary analysis are:

- SYSTANE BALANCE is superior to REFRESH OPTIVE Advanced with respect to change from baseline in TFBUT at Day 35
- SYSTANE BALANCE is superior to REFRESH OPTIVE Advanced with respect to LLT AUC₁₂₀ at Day 35

- SYSTANE BALANCE is superior to REFRESH OPTIVE Advanced with respect to change from baseline in Global Ocular Discomfort VAS score at Day 35

The null and alternative hypotheses for the first secondary endpoint are:

$$H_0: \mu_{SB} - \mu_{OA} \leq 0$$

$H_1: \mu_{SB} - \mu_{OA} > 0$ where μ_{SB} and μ_{OA} denote the mean change from baseline in TFBUT at Day 35 for SYSTANE BALANCE and REFRESH OPTIVE Advanced, respectively.

The null and alternative hypotheses for the second secondary endpoint are:

$$H_0: \mu_{SB} - \mu_{OA} \leq 0$$

$$H_1: \mu_{SB} - \mu_{OA} > 0$$

where μ_{SB} and μ_{OA} denote the mean LLT AUC₁₂₀ at Day 35 for SYSTANE BALANCE and REFRESH OPTIVE Advanced, respectively.

The null and alternative hypotheses for the third secondary endpoint are:

$$H_0: \mu_{SB} - \mu_{OA} \geq 0$$

[figure not shown]
$$H_1: \mu_{SB} - \mu_{OA} < 0$$

where μ_{SB} and μ_{OA} denote the mean change from baseline in VAS score at Day 35 for SYSTANE BALANCE and REFRESH OPTIVE Advanced, respectively.

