11.4.2.2 Analysis Methods

The analysis of the secondary efficacy parameter LLT AUC₁₂₀ at Day 35, and change from baseline in Global Ocular Discomfort VAS score at Day 35, and change from baseline of the TFBUT at Day 35 will be based on a MMRM. The mixed model will include terms for baseline parameter values, treatment, visit (Day 15, Day 35), and treatment-by-visit interaction. Estimates of the difference in mean change from baseline between SYSTANE BALANCE and REFRESH OPTIVE Advanced and associated 95% CIs will be presented.

Each endpoint will be evaluated for superiority of SYSTANE BALANCE over REFRESH OPTIVE Advanced. The p-value from the one-sided test less than 0.025 for a difference in favor of SYSTANE BALANCE will indicate superiority of SYSTANE BALANCE over REFRESH OPTIVE Advanced.

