Evidence of efficacy (non-inferiority) will be deemed established if the lower limit of the 95% CI (equivalent to the 1-sided 97.5% CI) for the adjusted estimate of the difference (SYSTANE BALANCE - REFRESH OPTIVE Advanced/ OPTIVE PLUS [UK]) is above - 1.0 second (non-inferiority margin). The non-inferiority margin was chosen as 1.0 second on the basis that an increase of at least 25% in the baseline TFBUT of a subject with lipid-deficient dry eye would be considered clinically meaningful since the subject would blink less often.

The analysis set for the primary efficacy assessment will be the PPS. As a sensitivity analysis, the analysis will be repeated for the FAS using the same model.

Observed values and change from baseline values for the analysis eye for the PPS and FAS will also be presented descriptively (N, mean, median, SD, standard error [SE], minimum, and maximum) at each study visit for each study treatment. A plot of mean change in TFBUT by study visit and study treatment with error bars representing +/- 1 SE will be presented using the analysis eye. The x-axis will be study visit and the y-axis will be the change in TFBUT from baseline.

Observed values from all visits for the RS will also be listed along with the following variables: treatment, investigator, subject, age, sex, race, ethnicity, visit, eye, baseline value, and value at the visit.

The analysis of the secondary efficacy parameters will also be based on a MMRM model. The mixed model will include terms for the respective baseline parameter value (continuous), study treatment (SYSTANE BALANCE, REFRESH OPTIVE Advanced/ OPTIVE PLUS [UK]), visit (Day 15 [Visit 2], Day 35 [Visit 3]), and study treatment-by-visit interaction. The same procedure as outlined for the primary efficacy analysis in selecting the best fitting covariance structure will be applied. Estimates of the difference in mean change from baseline between SYSTANE BALANCE and REFRESH OPTIVE Advanced/ OPTIVE PLUS (UK) and the associated 95% CIs in the analysis eye will be presented.

Each secondary endpoint will be evaluated for superiority of SYSTANE BALANCE over REFRESH OPTIVE Advanced/ OPTIVE PLUS (UK).

The analysis set for the secondary efficacy assessments will be the FAS. As a sensitivity analysis, the analysis will be repeated for the PPS using the same model.

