5.3.1 Multiplicity Strategy

To ensure overall control of the type I error rate, following the rejection of the primary efficacy null hypothesis (if the lower limit of the 95% CI [equivalent to the 1-sided 97.5% CI] for the difference of the primary efficacy endpoint is above -1.0 second), the secondary hypotheses will be tested using the Hochberg testing procedure.

For the secondary efficacy endpoints, let:

- H_{0i} refers to the corresponding null hypotheses
- p_i refers to the p-values for H_{0i} , which will be calculated without any multiplicity adjustment where $i = 1, \dots, k$ such that $[1], \dots, [k]$ refer to the order from $p_{[1]} \leq \dots \leq p_{[k]}$.
- Hochberg’s step-up method will proceed as follows:
 - Step 1: If $p_{[k]} < \alpha$ (where α is 0.025, 1-sided), reject all H_{0i} (where $i = 1, \dots, k$), and stop; otherwise go to Step 2.
 - Step 2: If $p_{[k-1]} < \alpha/2$ (where α is 0.025, 1-sided), reject $H_{0[i]}$, $i = 1, \dots, k - 1$, and stop; otherwise go to Step 3.

- ...
- Step k: If $p_{[i]} < \alpha/k$ (where α is 0.025, 1-sided), reject $H_{0[i]}$, $i = 1$, and stop.

Both the adjusted and unadjusted p-values for the secondary efficacy endpoints will be presented.

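### SAP 5.2 prints the VAS superiority hypotheses with the signs reversed, so the one-sided test taken literally would credit a worse discomfort outcome

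*SAP*

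**What the plan says.** SAP 5.2 lists two secondary superiority hypotheses, one for TFBUT and one for Global Ocular Discomfort VAS. Under the VAS bullet the two means "denote the mean change from baseline in Global Ocular Discomfort VAS score at Day 35 (Visit 3) in the analysis eye", the null is SB − OA ≤ 0 and the alternative is "H_1: \mu_{SB} - \mu_{OA} > 0". The same pair stands under TFBUT, where it is correct.

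Protocol 11.4.2.1 gives the VAS change at Day 35 a null of SB − OA ≥ 0 and the alternative "H_1: \mu_{SB} - \mu_{OA} < 0". Protocol 11.4.2.2 adds a decision rule: "The p-value from the one-sided test less than 0.025 for a difference in favor of SYSTANE BALANCE will indicate superiority".

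SAP 5.3 keeps only part of that rule: "Each secondary endpoint will be evaluated for superiority of SYSTANE BALANCE over REFRESH OPTIVE Advanced", with the UK product name added. SAP 5.3.1 then runs Hochberg on the secondary endpoints. There H_0i "refers to the corresponding null hypotheses", p_i is the p-value for H_0i, and the level is given as "where α is 0.025, 1-sided".

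**The concern.** The sign of the alternative fixes which tail of the VAS comparison counts as success. SAP 5.1 builds the score as the square root of discomfort frequency times discomfort severity, and SAP section 2 defines change as post-baseline minus baseline. Improvement is therefore a negative change, and a positive SB − OA means that SYSTANE BALANCE did worse than the comparator. On these definitions the SAP's alternative describes inferiority, although its own bullet says superior.

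Two things are at stake, both conditional on the one-sided p-value being derived from the symbols in 5.2:

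- The VAS claim is reversed. A real advantage could not be declared, and a real disadvantage could be declared superiority in a multiplicity-controlled test.
- The TFBUT superiority claim becomes harder to win. A real VAS advantage would give a p-value near 1, Hochberg's first step would fail, and TFBUT would have to meet 0.0125 instead of 0.025.

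**Working it through.** **Direction, side by side**

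| Source | Null | Alternative |
|---|---|---|
| Protocol 11.4.2.1, VAS | SB − OA ≥ 0 | SB − OA < 0 |
| SAP 5.2, VAS | SB − OA ≤ 0 | SB − OA > 0 |
| SAP 5.2, TFBUT | SB − OA ≤ 0 | SB − OA > 0 |

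Both VAS rows concern the mean change in VAS at Day 35. SAP 11.1 lists one change to the protocol's analyses, the listing-only treatment of LLT, so the reversal is not declared. The code in SAP 12.1.1 requests least-squares means with differences and confidence limits and sets no tail. Someone must therefore convert two-sided output to a one-sided p-value, and 5.2 holds the SAP's only formal statement of the VAS direction.

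**The plan's own figure**

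SAP section 9 gives 200 evaluable subjects for 80% power in the primary test (difference 0.0, SD 2.5, margin 1.0, one-sided 0.025). With 100 per arm, 1.0 / (2.5 × √(2/100)) = 2.828, and power = Φ(2.828 − 1.960) = 80.7%. The noncentral-t version gives 80.4% and a required total of exactly 200, so the plan's figure reproduces. The documents give no VAS SD, effect or power.

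**VAS test in each direction**

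Inputs: 100 per arm (the evaluable target), one-sided 0.025, normal approximation. The true difference of d SD is an assumption, shown as a range. For a true advantage:

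- protocol direction: 1 − Φ(1.960 − d/√(2/100))
- SAP direction: 1 − Φ(1.960 + d/√(2/100))

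| True VAS advantage | Declared superior, protocol signs | Declared superior, SAP signs |
|---|---|---|
| 0.2 SD | 29.3% | 0.04% |
| 0.3 SD | 56.4% | 0.002% |
| 0.4 SD | 80.7% | below 0.001% |
| 0.5 SD | 94.2% | below 0.001% |

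For a true disadvantage of the same size the two columns swap. At zero difference both directions reject 2.5% of the time.

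A single result shows the same thing. A VAS z of −2.5, favouring SYSTANE BALANCE, gives p = 0.0062 in the protocol direction and p = 0.9938 under the SAP's null.

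**Carry-over to TFBUT through Hochberg (two hypotheses)**

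Suppose TFBUT has one-sided p = 0.02 and VAS has z = −2.5.

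- Protocol signs: the larger p is 0.02, below 0.025, so both nulls are rejected.
- SAP signs: the larger p is 0.9938, so step 1 fails. The smaller p, 0.02, is not below 0.0125, so neither null is rejected.

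For power, assume independent tests, TFBUT power of 80% at 0.025 (hence 71.2% at 0.0125) and VAS power of 80% in the protocol direction:

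- protocol signs: 0.712 + (0.800 − 0.712) × 0.80 = 0.782
- SAP signs: 0.712

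The loss is 7.0 points. It is 4.4 points with VAS power of 50% and 7.9 with 90%. With correlation 0.5 and VAS power of 80% it is 6.3 points (0.775 against 0.712).

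The documents assume a TFBUT difference of 0.0, where there is no superiority power to lose. With VAS power of 80.7% the TFBUT rejection rate there would be 0.0125 + 0.0125 × 0.807 = 2.3% with the protocol signs and 1.25% with the SAP signs.

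**The case against.** The strongest answer is that the intended direction is plain in words. SAP section 1 says the document describes the analyses planned in protocol section 11, which holds the correct signs and the rule on a difference favouring SYSTANE BALANCE. The SAP's VAS bullet, section 5.3 and Table 5–1 all speak of superiority, and the reported difference with its 95% CI would show which arm did better. On this view it is a block copied from TFBUT that a competent programmer would catch.

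Much of that stands. A copying slip is the likely explanation, and harm arises only if the symbols are followed over the word. It does not remove the error. SAP section 1 also allows for deviations from the protocol, so it sets no rule of precedence. SAP 5.3 leaves out the protocol's phrase on direction, and 5.3.1 defines each one-sided p-value by its printed null.

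Three smaller points are also fair. The Hochberg loss rests on an assumed TFBUT advantage that the documents do not make. The FAS, which carries the superiority inference, could reach about 110 per arm (220 / 2), which raises the 0.4 SD figure from 81% to 84%. And correcting the two symbols alone would repair the formal definition; the further wording is a safeguard.

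**Conclusion.** The concern holds. The VAS hypotheses in SAP 5.2 are reversed relative to protocol 11.4.2.1 and to the SAP's own claim of superiority, and the reversal is not a declared change.

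Executed literally, the rule would almost never declare a true VAS advantage and would credit a disadvantage with the power meant for a benefit: 56% to 94% for assumed differences of 0.3 to 0.5 SD. The knock-on for TFBUT superiority is about 4 to 8 points of power when TFBUT has 80% power at 0.025 and the tests are independent.

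The scale anchors are not printed. That a higher score is worse is inferred from how the score is composed and from the protocol's own alternative. The primary non-inferiority test, its margin, the sample size, and the VAS estimate with its CI are unaffected. This should be fixed, but it does not threaten the primary conclusion.

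**What to change.** In SAP 5.2, replace the VAS pair with H0: μ_SB − μ_OA ≥ 0 and H1: μ_SB − μ_OA < 0, to match protocol 11.4.2.1. In 5.3.1, state that a lower VAS is better, that the VAS one-sided p-value is the lower tail of SB − OA, and that the TFBUT one is the upper tail. In 5.3, restore the protocol's condition that the difference must favour SYSTANE BALANCE.

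A minor tidy-up in the same edit is to review the analysis-eye wording for VAS. SAP 2.1 treats VAS as subject-reported, and SAP 4.2 does not mark it as eye-specific.

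The cost is SAP wording and one check of how the one-sided p-values are derived. SAP 11.1 records that the database is not yet locked and the treatment code is unbroken, so this can be done before unmasking. Made after unmasking, a change of tail would look data-driven.
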